3. INTRODUCTION

This Statistical Analysis Plan is intended to describe the planned statistical analysis of study 1407-004.

3.1 Background and Rationale

Prismocitrate 18 Solution is intended to be used as a replacement solution for regional anticoagulation of the extracorporeal circuit in acute kidney injury (AKI) patients treated with continuous renal replacement therapy (CRRT). Prismocitrate 18 is a CRRT solution developed by Gambro AB (now part of Baxter Healthcare Corporation) for use as both a replacement solution and an anticoagulant to prevent clotting of the extracorporeal circuit. Regional citrate anticoagulation (RCA) has been in use for renal replacement therapy (RRT) since 1961¹ for conventional hemodialysis (HD) and for CRRT since 1990². Multiple publications in the literature document the use of RCA in RRT and CRRT. Recent meta-analyses of randomized controlled trials demonstrate benefits for RCA over standard heparin anticoagulation with respect to bleeding and circuit longevity in AKI patients treated with CRRT. ³⁻⁸

The mechanism underlying the efficacy of citrate as an extracorporeal anticoagulant is chelation of calcium, an integral physiologic component of the clotting cascade. During CRRT with RCA, delivery of citrate to the "arterial" blood prior to the CRRT filter results in chelation of calcium, rendering blood passing through the filter effectively anticoagulated. After blood leaves the filter in the "venous" bloodline, the anticoagulant effect is reversed when the citrate containing blood is returned to the patient. The ionized calcium levels in the patient are maintained within normal levels by a calcium infusion. Due to the pivotal role played by calcium, frequent monitoring of both systemic (patient) and post-filter blood ionized calcium (iCa) concentrations is typically performed during RCA. Post-filter blood iCa concentration is considered an appropriate surrogate for assessing the level of anticoagulation achieved.

Continuous renal replacement therapy comprises several different therapies used primarily for the management of AKI patients. These therapies differ with respect to the primary mechanism for solute removal (ie, diffusion and/or convection). The modality to be applied in this trial will be continuous venovenous hemodiafiltration (CVVHDF) in which solute clearance occurs by both diffusion and convection, achieved by the use of dialysate and replacement fluid, respectively. Prismocitrate 18 will serve as a replacement and anticoagulation solution containing citrate as both an anticoagulant and buffer source, the latter being necessary for the treatment of metabolic acidosis that routinely accompanies AKI or other serious conditions in CVVHDF, use of a cleared

bicarbonate-containing dialysate not only provides additional solute clearance but also specifically affords the capability to modulate acid-base balance with changes in dialysate flow rate or composition.

4. TRIAL OBJECTIVES

4.1 Primary Objectives

The primary objective of this study is to evaluate the efficacy of Prismocitrate 18 in prolonging extracorporeal circuit life in patients treated with CRRT. The Control Group will be patients receiving CRRT with no anticoagulation.

4.2 Secondary Objectives

The secondary objectives of this study are to evaluate the efficacy of Prismocitrate 18 in achieving appropriate anticoagulation through assessments of systemic and post-filter blood iCa concentrations, and to evaluate the efficacy of using Prismocitrate 18 in delivering the prescribed CRRT dose, with delivered dose based on total (daily) effluent volume and expressed as mL/kg/hour. Additionally, the safety profile will be evaluated through assessments of metabolic parameters, including serum bicarbonate, pH, base excess, iCa, total calcium, magnesium, chloride and other relevant serum electrolytes along with anion gap. The potential for the development of citrate accumulation will be evaluated specifically through assessment of the total calcium/iCa²⁺ ratio (both measurements in mmol/L), anion gap and base excess (along with pH). Finally, the potential for bleeding events (number, location, duration), and the number and type of blood transfusions along with the number of units infused will also be assessed.

From the functional perspective, another secondary objective is to complete training on administration of Prismocitrate 18 and demonstrate the understanding of the user groups on how to use the solution by passing an assessment at the end of training. The user groups who need to be assessed prior to use of Prismocitrate 18 in the clinical trial setting will be comprised of physicians, nurses, and other clinicians who may be part of prescribing, initiating, or modifying treatment during the 120 hours evaluation period.

4.3 Exploratory Objectives

Not applicable.

5. STUDY DESIGN AND CONDUCT CONSIDERATIONS

5.1 Study Design

This study is a multi-center, prospective, non-blinded, one to one randomized study. A total of 160 adult patients, 80 in each study arm, will be enrolled at up to 15 investigational sites in the United States (US) and Canada. Patients meeting all of the inclusion criteria and none of the exclusion criteria of this protocol, and deemed treatable by either CRRT with Prismocitrate 18 solution or CRRT with no systemic anticoagulation, are eligible for enrollment in the study. If a patient is already receiving standard-of-care CRRT, they must be randomized within 24 hours of initiation of their standard-of-care CRRT. All patients will be treated with predilution CVVHDF as the study CRRT modality. Patients enrolled in the study will receive either Prismocitrate 18 anticoagulation or no systemic anticoagulation during their study CRRT, and extracorporeal circuit life will be monitored for up to 120 hours of study CRRT (treatment period). During the treatment period, the adequacy of anticoagulation in the Prismocitrate 18 patients will be assessed by monitoring extracorporeal circuit pressures and by assessment of systemic and post-filter blood iCa concentrations. Patients will be monitored for acid-base parameters and serum electrolytes at baseline prior to any CRRT), initiation (after randomization but before the initiation of study CRRT) and at pre-determined intervals during treatment. Information on bleeding events (number, location, duration) and the number and type of blood transfusions along with the number of units infused will also be collected.

5.1.1 Baseline Definition

Baseline (BL) will be defined as the last measurement before the initiation of CRRT. If a patient has not been on standard-of-care CRRT, the Baseline and Initiation labs will be the same. In this case, the acceptable baseline laboratory measurements can be up to 1 hour after initiation of CRRT.

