5.2 Treatment Administered

All patients in this study will be treated with the Prismaflex System Control Unit with Version 7.xx Software and the disposable Prismaflex M150 Set. The patients will be followed post-randomization for up to 120 hours from the initiation of study CRRT. This 120 hour post-randomization period will be referred to as the Treatment Period. At the time of randomization, if a patient is currently receiving CRRT, the standard-of-care CRRT extracorporeal circuit will be replaced with a new Prismaflex M150 Set. During the Treatment Period, patients will be treated up to 120 hours of study CRRT with either Prismocitrate 18 or no systemic anticoagulation. "Baseline" during the Treatment Period is defined as prior to any CRRT therapy, "Initiation" is defined as after randomization but before the initiation of study CRRT. Initiation may occur at the same time point as baseline, should enrollment and randomization occur prior to any CRRT therapy. Following data points will be collected during study CRRT for the duration of the Treatment Period:

- Extracorporeal circuit pressures will be measured and recorded by the Prismaflex System device in real time. The end of the extracorporeal circuit life will be defined by the occurrence of one or both of the following Prismaflex System alarms/conditions, if the alarms cannot be mitigated. At this point study CRRT will be terminated and the extracorporeal circuit replaced, because mitigation of the following alarms is not possible:
 - "Warning: Filter Clotted", and/or
 - "Advisory TMP Too High"

Note: The nurse at the clinical site will document the alarm and rationale to stop treatment on the eCRF. In addition, the Prismaflex logging information from the data cards (one card per patient) will be collected on an ongoing basis and anonymized data will be sent to Baxter for technical analysis. An Independent Adjudicator will make the final determination of the alarm cause (see Section 9.9 Primary Endpoint Adjudication).

- Serum bicarbonate and pH will be measured at baseline, initiation of study CRRT, at 6 hour intervals and at 120 hours or end of the Treatment Period (see Appendix 1).

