5.2.3 Monitoring of Therapy

Systemic iCa levels will be measured at baseline, initiation, and systemic and post-filter blood iCa levels will be measure 1 hour after initiation of study CRRT (post-randomization) and then every 6 hours thereafter and at 120 hours or end of Treatment Period. The pH and bicarbonate should be measured at baseline, initiation, and every 6 hours during the 120 hour Treatment Period and at 120 hours or end of Treatment Period. Health care professionals managing the patient should be instructed to notify the clinician immediately if the serum pH is < 7.20 or > 7.45, serum bicarbonate is < 15 or > 35 mmol/L, and/or the systemic blood iCa is < 0.9 or > 1.3 mmol/L.

Citrate metabolism may be impaired in patients with moderate to severe liver failure. The additional steps outlined below are needed to monitor specifically for the potential development of citrate accumulation, not only in these patients but in the entire study

population. Blood total calcium concentrations will be measured at baseline, initiation, 1 hour and every 6 hours during the 120 hour Treatment Period and at 120 hours or end of the Treatment Period from the initiation of study CRRT. In conjunction with simultaneous systemic iCa concentrations, the total calcium/iCa ratio (both measurements in mmol/L) will be determined as an indicator of citrate accumulation and health care professionals managing the patient should be instructed to notify the clinician for any value above 2. 1. Moreover, based on the clinical judgement of the managing physician, this threshold value should also prompt an immediate CRRT prescription change designed to correct the metabolic disturbance. One of the following prescription changes should occur:

- Decrease in the Prismocitrate infusion rate; or
- Increase in the BFR; or
- Increase in the dialysate flow rate

The effect of one of these changes should be assessed with ongoing monitoring of relevant clinical and laboratory parameters - if improvement does not occur within two (2) hours, the Prismocitrate infusion should be stopped.

When a total calcium/iCa ratio of more than 2.1 is reported, any one of the following abnormalities reported concurrently should heighten the clinical suspicion of citrate accumulation and reinforce the need to undertake the steps outlined above:

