ABG=arterial blood gases; ALT=alanine transaminase; AST=aspartate transaminase; ALP=alkaline phosphatase; CBC=complete blood count; CRRT=continuous renal replacement therapy; iCa2+=ionized calcium; BUN=blood urea nitrogen, PT=prothrombin time; INR=international normalized ratio; PTT=partial thromboplastin time; VBG=venous blood gases

a If patient has not been on standard-of-care CRRT, the Baseline and Initiation labs are the same. If patient has been on standard-of-care CRRT for < 24 hours the Baseline labs are those collected prior to the standard-of-care CRRT with exception of systemic iCa2+, which blood must be drawn 1 hour prior to initiation of Study CRRT. For Baseline Labs the acceptable blood draw window is - 24 hours. For Initiation Labs, the acceptable blood draw window is \pm 1 hour.

b Acceptable blood draw window for Serum bicarbonate, pH, Systemic & Post-Filter iCa2+, Blood total calcium, Total calcium/ iCa²⁺ ratio and Serum electrolytes (sodium, potassium, chloride, phosphate, magnesium, anion gap and base excess) is ± 1 hour.

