- ^a If patient has not been on standard-of-care CRRT, the Baseline and Initiation labs are the same. If patient has been on standard-of-care CRRT for < 24 hours the Baseline labs are those collected prior to the standard-of-care CRRT with exception of systemic iCa²⁺, which blood must be drawn 1 hour prior to initiation of Study CRRT. For Baseline Labs, the acceptable blood draw window is 24 hours. For Initiation Labs, the acceptable blood draw window is \pm 1 hour.
- ^b Acceptable blood draw window for serum bicarbonate, pH, systemic & post-filter iCa2⁺, blood total calcium, total calcium/ iCa²⁺ ratio and serum electrolytes (sodium, potassium, chloride, phosphate, magnesium, anion gap and base excess) is \pm 1 hour.
- ^c If a parameter has not been measured when study CRRT was terminated, the last available measurement collected during the treatment period will be used as the end of study measurement

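### SAP 5.1.1 lets laboratory values drawn up to 1 hour after CRRT starts serve as baseline, and the sampling footnote leaves the baseline total calcium/iCa ratio open to non-simultaneous values

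*SAP*

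**What the plan says.** SAP 5.1.1 opens with "Baseline (BL) will be defined as the last measurement before the initiation of CRRT". Two sentences later, for patients not previously on standard-of-care CRRT, it adds that "the acceptable baseline laboratory measurements can be up to 1 hour after initiation of CRRT".

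Protocol 5.2 is stricter. Baseline "during the Treatment Period is defined as prior to any CRRT therapy", and Initiation "is defined as after randomization but before the initiation of study CRRT". In Protocol Appendix 1 and SAP Table 2, both samples sit in the column for the time between randomization and the start of study CRRT.

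Footnote a of those tables adds three rules:
- "If patient has not been on standard-of-care CRRT, the Baseline and Initiation labs are the same".
- "For Initiation Labs, the acceptable blood draw window is" plus or minus 1 hour.
- Patients entering from standard-of-care CRRT take their Baseline labs from before that CRRT, "with exception of systemic iCa2+, which blood must be drawn 1 hour prior to initiation of Study CRRT".

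Protocol 5.2 separately requires systemic iCa in the Prismocitrate arm 1 hour before study CRRT. On the ratio, Protocol 5.2.3 says: "In conjunction with simultaneous systemic iCa concentrations, the total calcium/iCa ratio (both measurements in mmol/L) will be determined".

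**The concern.** Baseline is the reference for the change-from-baseline comparisons in Protocol 8.6 and a covariate in the mixed models and ANCOVA of SAP 13.3, 14.3 and 14.4. If it may be drawn after treatment has begun, the reference can already contain part of the effect being measured. Controls receive no citrate, so the citrate-specific part of that effect falls in one arm only.

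The second issue concerns patients entering from standard-of-care CRRT. The total calcium/iCa ratio is the plan's indicator of citrate accumulation, flagged above 2.1. A ratio whose two components come from different times, one before any CRRT and one during it, is not the quantity that the threshold was set for.

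**Working it through.** There is no plan figure to reproduce. The check is arithmetic on the documents' own sampling windows.

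**Patients with no prior CRRT.** Time 0 is the start of study CRRT, which for them is the start of any CRRT.
- Initiation window, hence the baseline window under the SAP allowance: -1 to +1 h (footnote a).
- 1-hour calcium sample: nominal 1 h, plus or minus 1 h (footnote b), so 0 to 2 h.
- First sample for pH, bicarbonate, base excess, electrolytes and anion gap: 6 h plus or minus 1 h, so 5 to 7 h.

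Overlap = min(upper limits) - max(lower limits), or 0 if negative.
- Against the 1-hour sample: min(1, 2) - max(-1, 0) = 1 h.
- Against the 6-hour sample: min(1, 7) - max(-1, 5) = -4, so 0.

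A total-calcium draw in the first hour therefore meets both definitions, and its change from itself is zero. For the other analytes a double count is impossible, but an on-treatment baseline is still allowed. If the Initiation window ends at 0, the overlap becomes min(0, 2) - max(-1, 0) = 0.

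*Could an hour matter?* At the minimal initial rate in Protocol 5.2.2.5, 1 L/h x 18 mmol/L x 1 h = 18 mmol of citrate has entered the circuit by +1 h. Some leaves in the effluent, so this is not the dose reaching the patient. It shows only that the arms already differ by then.

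*Size of the bias.* Let p be the share of an arm with a post-start baseline and d the mean shift in those patients by the time of the draw. Mean change in that arm is displaced by -p x d, and the raw between-arm difference by -(p_P x d_P - p_C x d_C). In a model that adjusts for baseline, the spurious baseline difference enters multiplied by the baseline slope. The documents give neither p nor d. If p were 10% to 50% (an assumption), the displacement in an arm would be 0.1d to 0.5d in magnitude, with its sign depending on d.

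**Patients entering from standard-of-care CRRT.** Inclusion criterion 6 allows up to 24 h of that CRRT before randomization. Under footnote a:

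Gap between total calcium and iCa = (hours of standard-of-care CRRT) + (hours from randomization to study start) - 1 + (hours by which the baseline draw preceded standard-of-care CRRT).

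With study CRRT starting at randomization:

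| Prior CRRT | Drawn just before it began | Drawn 24 h before it began |
|---|---|---|
| 6 h | 6 + 0 - 1 + 0 = 5 h | 29 h |
| 12 h | 11 h | 35 h |
| 24 h | 23 h | 47 h |

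The last column applies only if the 24-hour Baseline window runs back from the start of standard-of-care CRRT; its reference time is not stated. Any delay from randomization to study start adds to every entry.

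*Illustration (assumed values).* Suppose the simultaneous ratio is 2.0 and iCa then falls 5% before its draw: 2.0/0.95 = 2.105, just above 2.1. If iCa rises 5%, 2.0/1.05 = 1.905. The error can go either way.

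**The case against.** The strongest reply is that most of the possible harm is contained elsewhere in the plan. Much of that stands.

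- **Systemic iCa.** A reader might infer that the iCa comparison is biased in the citrate arm. The documents do not support this. Protocol 5.2 requires that arm's iCa 1 hour before study CRRT, and the iCa row of the sampling table repeats the timing. Protocol 8.5.2 also models iCa as change from initiation, with separate models by prior CRRT if justified. Neither rule protects the other analytes.
- **Direction.** A reader might infer that later changes will look too small. That needs the early and later shifts to have the same sign. Calcium replacement is adjusted during treatment, so an early shift may reverse. The allowance also covers controls, so the early effect of CRRT itself can enter both arms.
- **The ratio.** A reader might take the mixed-time ratio as a settled rule. The exception in footnote a names systemic iCa only, the ratio has its own table row, and Protocol 5.2 and 5.2.3 call for simultaneous values. If CRRT in SAP 5.1.1 means study CRRT, the mismatch may disappear. The passages conflict, and none decides the matter.
- **Hidden accumulation.** A reader might infer that a wrong baseline ratio masks on-treatment rises. SAP 14.3 summarizes the ratio only descriptively and counts values above 2.1 at each time point in absolute terms. A baseline error cannot remove an on-treatment flag.

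None of this answers the contradiction within SAP 5.1.1 for total calcium, pH, bicarbonate, base excess, electrolytes and anion gap.

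**Conclusion.** The main point holds. The SAP allowance and the plus or minus 1 hour Initiation window both permit an on-treatment baseline in patients with no prior CRRT, against the stated definitions. For total calcium the baseline and 1-hour windows share a full hour. How many patients would be affected, and by how much, cannot be derived from the documents. This is what the rules permit, not what every patient would have. Circuit life, the sample size and the type I error are untouched, so this is a correction that should be made, not a threat to the trial's main conclusion.

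The secondary point is a contradiction to reconcile. On the footnote reading the two components can be about 23 h apart, or about 47 h if the draw window runs back from standard-of-care CRRT. Its reach is the descriptive baseline ratio, the baseline count above 2.1 and the ratio's change-from-baseline column.

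**What to change.** 1. In SAP 5.1.1, delete the sentence that accepts values after CRRT has started, and state whether CRRT there means any CRRT or study CRRT.
2. In the analysis, classify every laboratory value timed after the start of study CRRT as on-treatment, whatever its nominal label.
3. In footnote a of Protocol Appendix 1 and SAP Table 2, end the Initiation window at the start of study CRRT.
4. Reconcile footnote a with Protocol 5.2 and 5.2.3 on the ratio. Compute the baseline ratio only when total calcium and iCa come from the same draw; otherwise set it to missing.

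Switching to the Initiation values does not by itself satisfy item 4. iCa is due 1 hour before start and, in the Prismocitrate arm, may be replaced by a corrected value, while Initiation total calcium has its own window. No passage says the two share a draw.

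The cost is wording in the SAP and two footnotes. A few patients whose only draw came after the start would lose a baseline value, and some ratio baselines would be missing. SAP 8.2 rules out imputation, so these patients would drop out of the baseline-adjusted models for the analytes concerned; their number should be reported by arm. No new sampling time is needed.

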5.2 Sample Size

A sample size of 80 patients in each treatment group will provide > 90% power for assessing the equality of the extracorporeal circuit life between treatment groups using a two-sided clustered log-rank test with an overall alpha level of 0.050. This is based on the following assumptions: median circuit lives of and in the Prismocitrate 18 and Control group, filters per patient (during the Evaluation period of 120 hours) in the Prismocitrate 18 and Control group, of subjects discontinuing therapy for reasons other than due to clotting of the circuit (i.e., common exponential dropout rate of), a single interim analysis when 50% of patients have

completed treatment, and combination of results from the two study stages (prior to vs after interim analysis) using Fisher's combination test⁹.

5.3 Randomization Procedure

All enrolled subjects will be randomized to one of two treatment arms (Prismocitrate 18 or Control Group) in a 1:1 manner using a site-stratified central randomization scheme.

5.4 Schedule of Visits and Procedures

5.4.1 Schedule of Events

The schedule of events is presented below in Table 1.

Table 1 Schedule of Events

Evaluation	Screening and Baseline	During Study CRRT Treatment Period	End of Study CRRT During Treatment Period
Informed Consent	X		
Demographics, Medical and Medication Histories ^a	X		
Physical Examination	X		X
Height and BMI	X		
Weight ^b	X	X	X
Vital Signs	X		X
Randomization ^c	X		
Prismaflex System Information ^d		X	
Prismaflex M150 Set Information and Extracorporeal Circuit Assessment ^e		X	
Blood Access Information ^f		X	
CRRT Treatment Modality ^g		X	
CRRT Treatment Prescription ^h		X	
Priming Solution ⁱ		X	
Replacement Solution Prescription ⁱ		X	
Dialysate Prescription ⁱ		X	
Anticoagulation Information ^j		X	
Clinical Laboratory Evaluations ^k		X	X
Blood Pressure and Mean Arterial Pressure ^l	X	X	X
Effluent Volume (in ml) ^m		X	X
AEs/SAEs		X	X
Concomitant Medications		X	X
Bleeding Events ⁿ		X	
Transfusions ^o		X	
Patient Fluid Removal ^p		X	

·

Evaluation	Screening and Baseline	During Study CRRT Treatment Period	End of Study CRRT During Treatment Period
Evaluation	Daseille	Treatment reriou	renou

- ^a Demographics will include gender, illness severity score, chronological age at consent, pre-study CRRT weight and height. Medical history will include indication for CRRT, known allergies, past/present conditions as well as surgical procedures. Medication history will include all medications taken and/or prescribed during the 7-day window prior to informed consent and those relevant to ICU admission.
- ^b In addition to the pre-study CRRT weight, during the treatment period, daily weight will need to be obtained and recorded/entered each morning (eg, at 8:00 am) in the "System Tools" screen.
- ^c All enrolled subjects will be randomized to one of two treatment arms (Prismocitrate Group or Control Group) in a 1:1 manner using a central randomization scheme.
- ^d Prismaflex System information will include collection of the Prismaflex System serial number as well as the date and time of study CRRT initiation and termination (each event over the 120 hours treatment period). This will include recording all disruptions in treatment (eg, circuit clotting, machine malfunction, patient required treatment/diagnostic tests external to ICU).
- ^e Prismaflex M150 Set information will include the sequential set number, product lot number, date and time for installation and replacement, and the reason for replacement. The end of the extracorporeal circuit life will be defined by time at which one or both of the following Prismaflex System alarms/conditions occur after which the study CRRT treatment will be terminated and the patient will end the treatment period if mitigation of the following alarms is not possible: "Warning: Filter Clotted" and/or "Advisory TMP Too High".
- ^f Blood access information will include catheter-type, manufacturer, length & size, and catheter anatomical insertion location.
- ^g CRRT treatment modality will be confirmed as CVVHDF (Hemodiafiltration).
- h CRRT prescription will include patient fluid removal flow rate (mL/hour), post-filter replacement flow rate (mL/hour), PBP flow rate (mL/hour), BFR (mL/hour), dialysate flow rate (mL/hour), Prismocitrate 18 flow rate (mL/hour) and calcium gluconate or calcium chloride infusion details.
- ¹ Priming solution formulation, brand name/manufacturer; Dialysate and replacement solution prescription information will include the brand name/manufacturer, formulation, and volume. The initial prescription will be recorded along with any changes throughout the treatment period.
- ^j Anticoagulation information will include confirmation if the patient was randomized to 'Prismocitrate 18' or 'no systemic anticoagulation'.
- ^k Clinical laboratory evaluations are presented in detail in Table 2.
- ¹ Blood pressure including mean arterial pressure is collected at baseline (after randomization but before the initiation of study CRRT) and at 6 hour intervals during the treatment period up to 120 hours of study CRRT, as well as at End of Treatment.
- ^mEffluent volume (in mL) will be recorded from the Prismaflex System history screen. In the Prismaflex software, the starting time for the charting interval will be set (e.g., at 8:00 am) and the volumes and doses will be stored for each day starting at that time.
- ⁿ Bleeding events information will include number, location, duration, estimated blood loss, and adverse event data (if applicable).
- ^o All blood transfusions information will include: (number, type, and number of units infused), relevant laboratory parameters (i.e., hemoglobin/hematocrit and platelet values, etc.), as well as adverse event data (if applicable).
- ^p Patient Fluid Removal data collection will include post-treatment weight, the amount of fluid removed, and administration of input therapeutic fluids.

-

